#### **7.5.2. Sample Analysis**

Plasma analysis will be performed under the control of Platform Technology Sciences (PTS)-DMPK/Scinovo, GlaxoSmithKline, the details of which will be included in the Study Reference Manual (SRM). Concentrations of GSK2245035 will be determined in plasma samples using the currently approved bioanalytical methodology. Raw data will be archived at the bioanalytical site (detailed in the SRM).

Once the plasma has been analyzed for GSK2245035, any remaining plasma may be analyzed for other compound-related metabolites and the results reported under a separate PTS-DMPK/Scinovo, GlaxoSmithKline protocol.

### **7.6. Exploratory Biomarkers**

#### **7.6.1. Pharmacodynamic Markers**

Details for the collection of samples, processing, storage and shipping procedures for all samples are provided in the SRM. Time-points for all sample collections are shown in the Time and Events Tables (Section 7.1).

##### **7.6.1.1. PD blood samples**

Blood samples will be collected before and 24 hours post treatment on DV 1 and 8 for serum to measure blood PD biomarkers.

Blood will be collected before and 24 hours after treatment on DV 1 and 8 and prior to bronchial allergen challenges for preparation of peripheral blood mononuclear cells (PBMC). These samples may be used for CHIP cytometry for cellular subset phenotyping. If this biomarker analysis is performed it may be reported separately.

#### **7.6.1.2. Blood PAX collection**

Blood PAX samples for AFFYCHIP gene expression (mRNA transcriptome) will be collected before dosing on DV 1, 24 hours after DV 8 and prior to BAC on FUV2.

#### **7.6.1.3. PD nasal lavage samples**

Nasal lavage samples to measure PD biomarkers will be collected before and 24 hours post treatment on DV1, DV4 and DV8.

#### **7.6.1.4. Bronchial allergen challenge (BAC) associated biomarkers in induced sputum samples**

Sputum samples will be collected at the time points indicated in the time and events tables (see Section 7.1). Sputum sample collection at dosing/follow up visits is conditional on having obtained a sputum sample from the subject at screening.

Detailed information on collection, processing, storage and shipping procedures are provided in the SRM.

#### **7.6.1.5. Bronchial allergen challenge (BAC) associated biomarkers in blood samples**

Blood samples will be collected before, 6 hours and 24 hours after each BAC:

- For haematology, (WBC with differential) for blood eosinophil counts (before and 24 hours after BAC)
- To prepare PBMC that may be used for CHIP cytometry (before and 6 hours after BAC). If this biomarker analysis is performed it may be reported separately.

#### **7.6.1.6. Nasal allergen challenge associated biomarkers in nasal fluid samples**

Nasal filter and nasal lavage samples to measure exploratory biomarkers will be collected at the timepoints indicated in the Time and Events Tables, Section 7.1.

#### **7.6.1.7. Cellular profile of nasal mucosa**

Nasal scrapes may be collected after NAC following the completion of the collection of the 6 hour nasal lavage and nasal filter samples (at screening and at FUV1 and FUV2). Samples of suitable quality may be used for cellular analysis for example by CHIP cytometry or RNA-sequencing of single cells (if subjects have given informed consent for genetic analysis techniques). If this biomarker analysis is performed it may be reported separately.

### 7.6.2. Novel Biomarkers

With the subject's consent, nasal tissue, nasal fluid, sputum and blood samples will be collected during this study and may be used for the purposes of measuring novel biomarkers to identify factors that may influence the disease for study treatment, and/or medically related conditions, as well as the biological and clinical responses to GSK2245035. If relevant, this approach will be extended to include the identification of biomarkers associated with adverse events.

Samples will be collected at the time points indicated in the Time and Events Table Section 7.1. The timing of the collections may be adjusted on the basis of emerging pharmacokinetic or pharmacodynamic (PD) data from this study or other new information in order to ensure optimal evaluation of the PD endpoints.

Novel candidate biomarkers and subsequently discovered biomarkers of the biological response associated with asthma or medically related conditions and/or the action of GSK2245035 may be identified by application of:

- Measurement of the levels of a subset of RNA species on blood and sputum samples.
- Proteome analysis of plasma, nasal and sputum samples.

All samples will be retained for a maximum of 15 years after the last subject completes the trial.

### 7.7. Genetics

Information regarding genetic research is included in [Appendix 3](#).

## 8. DATA MANAGEMENT

- For this study, subject data will be entered into GSK defined CRFs, transmitted electronically to GSK or designee and combined with data provided from other sources in a validated data system.
- Paper diary subject data will be collected and transcribed into GSK defined CRFs by the site personnel.
- Management of clinical data will be performed in accordance with applicable GSK standards and data cleaning procedures to ensure the integrity of the data, e.g., removing errors and inconsistencies in the data.
- Adverse events and concomitant medications terms will be coded using MedDRA (Medical Dictionary for Regulatory Activities) and an internal validated medication dictionary, GSKDrug.
- CRFs (including queries and audit trails) will be retained by GSK, and copies will be sent to the investigator to maintain as the investigator copy. Subject initials will not be collected or transmitted to GSK according to GSK policy.

## **9. STATISTICAL CONSIDERATIONS AND DATA ANALYSES**

### **9.1. Hypotheses**

No formal hypotheses will be tested. The primary study objective will assess the effect of a weekly dose of 20ng GSK2245035 vs Placebo by precision estimation and credible intervals to estimate the magnitude of underlying effect sizes. A Bayesian approach will be utilised to obtain the posterior distribution for the mean treatment effects for the endpoints in the study (e.g. posterior distributions for percentage attenuation for the endpoint LAR: minimum FEV1 between 4-10 hours following allergen challenge one week after treatment.).

Other objectives will assess other pharmacodynamic effects and safety and tolerability of GSK 2245035.

### **9.2. Sample Size Considerations**

The following was performed for each of the proposed LAR primary endpoints:

[figure not shown]
- Success criteria: declare endpoint success if the posterior probability of any treatment attenuation exceeds 0.7.
- The probability of declaring a success has been computed for a range of true percent attenuations and sample sizes (n per arm equal allocation). To make the figures easier to interpret the “nuisance” parameters of the placebo response and the standard deviation have been accounted for as follows:
- Eight previous GSK BAC studies (Crossover design) have been re-analysed to obtain estimates of the average placebo response and the associated estimate of residual variability applicable to the proposed Parallel Group design.
- These estimates were combined in a random effects meta-analysis to obtain posterior distributions for the underlying parameter values (placebo average response, residual variability (for an individual subject) and a between study variance component). The future placebo response was computed as the sum of random draws from the posterior distributions of the placebo average response parameter and a normal distribution with mean zero and variance equal to the between study variance parameter. The future GSK2245035 response was derived using the simulation scenario’s true percentage attenuation. A pooled sample variance value was generated using a Chi-Square distribution with degrees of freedom appropriate to the simulation scenario and a sampled variance from the meta-analysis posterior distribution. Those numbers were entered into the standard formulae for power curves. Repeating this process 10,000 times and taking the median of the resulting power values constructs “Assurance” operational characteristics for the combination of true percent attenuation and sample size under evaluation.

- These assurance operational curves have been summarised graphically. The x-axis is a hypothetical true drug effect that is assumed to be known for experimental design purposes.
- The simulations can also be used to compute the minimum observed percentage attenuations that would result in a successful study outcome. The median (of the 10,000 simulations) have been derived for a variety of sample sizes and success criteria (probability thresholds 0.7, 0.75, 0.8, 0.85, 0.95) and displayed graphically. The y-axis is the observed effect from the study data.

[figure not shown]
Endpoint: LAR: minimum FEV1 between 4-10 hours following allergen challenge

- [Figure 1](#) illustrates the operating characteristics for the proposed design (n=20 completers per arm) that have a reasonable chance of meeting the definition of success.
- The best guess for the true treatment effect comes from the AZ study with AZD8848 in subjects with mild asthma, which dosed out of the allergen season and observed an approximately 18% effect size ([Figure 2](#)) [[Leaker](#) , 2012].

**Figure 1 LAR: minimum FEV1 between 4-10 hours following allergen challenge: Probability of Success (Assurance) with Success threshold of 0.7 (akin to a risk of false positives of 30%)**

[figure not shown]
**Figure 2** LAR: minimum FEV1 between 4-10 hours following allergen challenge: Minimum observed % attenuations needed to declare success for a variety of sample sizes and Success thresholds (levels of false positive risk)

[figure not shown]
- Endpoint: LAR: weighted mean FEV1 between 4-10 hours following allergen challenge

Figure 3 and Figure 4 are analogous to Figure 1 and Figure 2. The corresponding AZ point estimate was 27% attenuation. Similar conclusions can be drawn.

**Figure 3** LAR: weighted mean FEV1 between 4-10 hours following allergen challenge: Probability of Success (Assurance) with Success threshold of 0.7 (akin to a risk of false positives of 30%)

**Figure 4** LAR: weighted mean FEV1 between 4-10 hours following allergen challenge: Minimum observed % attenuations needed to declare success for a variety of sample sizes and Success thresholds (levels of false positive risk)

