**Table 2 Input data for Sample Size Work**

GSK Internal Study ID	LAR Minimum FEV1 between 4-10h			LAR Weighted Mean FEV1 between 4-10h		
	Average Placebo Response	Degrees of Freedom	Residual Variability	Average Placebo Response	Degrees of Freedom	Residual Variability
PPD	-1.3975	33.5	0.40571	-0.9462	33.1	0.30417
	-1.0864	45.9	0.13063	-0.7093	42.3	0.11430
	-1.1238	22.9	0.30521	-0.6916	22.8	0.18820
	-0.9006	48.9	0.07344	-0.3749	47.9	0.02191
	-0.7309	85.3	0.10717	-0.4662	84.4	0.07528
	-0.9027	31.9	0.27740	-0.5502	34.0	0.20925
	-1.4484	20.4	0.40528	-0.9817	20.3	0.31342
	-0.8129	69.6	0.15866	-0.5260	71.8	0.08695

Assuming the true treatment effect of GSK2245035 is no worse than the results from the AstraZeneca study and 20 subjects complete follow up assessments the probability of meeting the success criteria for Min LAR and WM LAR are approximately 78% and 81% respectively. This is considered sufficient justification for requiring 20 completers.

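### The stated probabilities of success (Min LAR 78%, WM LAR 81%) are medians of power; the probability itself is the mean, about 2 to 3 points lower for WM LAR and about 1 point lower for Min LAR

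*Protocol*

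**What the plan says.** Protocol 9.2 sets the rule for each primary endpoint: "declare endpoint success if the posterior probability of any treatment attenuation exceeds 0.7". Figures 1 and 3 describe this threshold as "akin to a risk of false positives of 30" per cent. The future placebo response is drawn from a random-effects meta-analysis of eight earlier crossover studies, including the between-study variance. The pooled variance is drawn from its own posterior and a chi-square distribution. Each draw goes into the standard power formula. The process is repeated 10,000 times, and "taking the median of the resulting power values constructs" what the protocol calls assurance. Figures 1 and 3 title the same quantity probability of success.

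Section 9.2.1 takes the AZ results as the true effect and 20 completers per arm, and states that "the probability of meeting the success criteria for Min LAR and WM LAR are approximately 78% and 81% respectively". It gives this as the justification for 20 completers. No mean of the power values is reported in either document.

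SAP 3.1 returns to the figure at the interim. The predicted probability of success is to be judged low or not relative to an operating characteristic of about 80% taken from the protocol.

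**The concern.** Each of the 10,000 power values is the probability of success for one set of nuisance values. By the law of total probability, the chance that this trial succeeds, when those values are themselves uncertain, is the average of the 10,000. The median answers another question: the power that half of the plausible settings exceed. The two agree only if the power values are roughly symmetric. Here they are not, because power near 80% has more room to fall than to rise. Calling the median a probability of success therefore errs in the favourable direction for both endpoints.

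At stake are the accuracy of the two figures that justify the sample size, and the benchmark that the interim prediction is compared with.

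**Working it through.** **Inputs**
- Success rule: posterior probability of any attenuation above 0.7. With non-informative priors this acts as a one-sided test at 0.30, so z = 0.524 (Protocol 9.2).
- Size: the "proposed design (n=20 completers per arm"), simulated with "sample sizes (n per arm equal allocation").
- True effects: Min LAR, the AZ study "observed an approximately 18% effect size"; WM LAR, "The corresponding AZ point estimate was 27% attenuation".
- Protocol Table 2, eight studies. Min LAR: mean placebo response −1.050, between-study SD 0.264, df-pooled variance 0.188. WM LAR: mean −0.656, SD 0.220, df-pooled variance 0.130.

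**Formula.** With attenuation a, placebo response P, standard deviation s and n = 20 per arm:

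power = Φ( a·|P| / (s·√(2/n)) − 0.524 )

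**Single-point check, no uncertainty**
- Min: 0.18 × 1.050 = 0.189; √(0.188 × 0.1) = 0.137; Φ(1.378 − 0.524) = 0.80.
- WM: 0.27 × 0.656 = 0.177; √(0.130 × 0.1) = 0.114; Φ(1.553 − 0.524) = 0.85.

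Both are near the stated figures. The values in Protocol 9.2.1 also carry nuisance uncertainty.

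**Why the median exceeds the mean.** Move the placebo response one between-study SD either way, holding the variance fixed:

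| Endpoint | Weaker placebo response | Centre | Stronger placebo response | Fall / rise (points) |
|---|---|---|---|---|
| Min | 0.69 (P = −0.786) | 0.80 | 0.89 (P = −1.314) | 11 / 8 |
| WM | 0.69 (P = −0.436) | 0.85 | 0.94 (P = −0.876) | 15 / 9 |

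The same shift costs more than it gains, and more so for WM. The distribution of power is left-skewed, so its mean lies below its median.

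**Full rebuild.** The Protocol 9.2 algorithm was run with 200,000 draws: a predictive placebo draw from a Bayesian random-effects meta-analysis, and a residual variance draw times chi-square(38)/38. The documents do not give the standard errors of the study means, the priors or the handling of variance heterogeneity, so these were varied:
- effective n for the standard errors equal to 1, 1/2, 1/3 or 1/4 of the degrees of freedom;
- two priors on the between-study variance;
- five treatments of the residual variance.

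Of these 40 variants, 24 reproduce both stated figures to within 2 points. In those 24:

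| | Stated | Median | Mean | Median − mean (points) | Direct simulation of success |
|---|---|---|---|---|---|
| Min LAR | 78% | 0.76–0.79 | 0.756–0.778 | 0.2–1.6, typically about 1 | 0.752–0.774 |
| WM LAR | 81% | 0.79–0.83 | 0.773–0.802 | 1.2–4.0, typically 2–3 | 0.771–0.797 |

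One such variant gives Min median 0.781 and mean 0.771, and WM median 0.816 and mean 0.789. The gap is larger for WM in every variant. A noncentral t power formula changes results by only about 0.3 points.

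The last column simulates the trial itself: it draws an observed effect and a sample variance, then applies the 0.7 rule. It lies within 0.5 points (WM) and 0.8 points (Min) of the mean, so the mean is what the design delivers.

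**Where the figure is used again.** In SAP 3.1 the predicted end-of-study success is the count of successful simulated iterations divided by all iterations, which is a mean. It is compared with the protocol's figure of about 80%, which is a median. The lookup tables (Protocol 9.3.2, SAP 3.1) are different: there a median is compared with the original operating characteristic, also a median.

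**The case against.** The strongest reply is that nothing is hidden. The protocol says that it takes the median, puts the word assurance in quotation marks for that construction, and uses medians throughout its simulations. The stated figures are reproducible as medians. A reader might infer an arithmetic slip, but the documents show a disclosed choice of summary that is later given the wrong name. That part of the reply stands.

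The size is also modest. The Min LAR gap disappears in the rounding of an approximate 78%. No target such as 80% is set, and about 78% was accepted for Min LAR, so a WM LAR figure of 77–80% would hardly have been refused. That stands too.

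A reader might further infer that the interim lookup tables are biased. The documents do not support this. Those tables compare like with like and allow a 10% margin, and no cell has been shown to change. The benchmark of about 80% belongs to a rule that SAP 3.1 itself calls non-binding, with no numerical cut-off. There is a mismatch between mean and median at that point, but its practical weight is small.

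The reply does not rescue the label. Section 9.2.1 states a probability that the simulation, as summarised, does not estimate, and the difference is in the favourable direction.

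**Conclusion.** The point holds as a modest overstatement under a wrong label. The probability of meeting the success criterion is about 77–80% for WM LAR, against 81% stated: typically 2 to 3 points lower, and 1 to 4 across plausible rebuilds. For Min LAR it is about 76–78% against 78%, which is within rounding.

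These ranges rest on Table 2, on a true effect equal to the AZ estimate, and on assumed standard errors and priors that the documents do not report. They show direction and approximate size and are not replacement values; those can come only from the sponsor's stored simulations. The direction of the gap is specific to power near 80% and need not hold at low attenuations.

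A reader might conclude that 20 completers per arm is too few. That does not follow, because no change to the sample size has been shown.

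**What to change.** From the stored simulations, take the mean of the 10,000 power values and report it as the probability of success (assurance) in Protocol 9.2 and in Figures 1 and 3. Restate the two percentages in 9.2.1 with the sponsor's own means. If the medians are kept, label them median power.

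In SAP 3.1, use the mean as the benchmark for the predicted probability of success, so that both sides of that comparison are proportions of successes. The lookup tables can stay as they are, provided that their text says that both quantities are medians.

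The cost is one summary function in existing output, edited text and figure labels, and a slightly less favourable number for WM LAR. No new simulation or change in design is needed.

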### 9.2.1. Sample Size Assumptions

The sample size assumes that the behaviour of the placebo response and the variability of the endpoints in this study are similar to the eight historical GSK studies (Table 2).

**Table 2 Input data for Sample Size Work**

GSK Internal Study ID	LAR Minimum FEV1 between 4-10h			LAR Weighted Mean FEV1 between 4-10h		
	Average Placebo Response	Degrees of Freedom	Residual Variability	Average Placebo Response	Degrees of Freedom	Residual Variability
PPD	-1.3975	33.5	0.40571	-0.9462	33.1	0.30417
	-1.0864	45.9	0.13063	-0.7093	42.3	0.11430
	-1.1238	22.9	0.30521	-0.6916	22.8	0.18820
	-0.9006	48.9	0.07344	-0.3749	47.9	0.02191
	-0.7309	85.3	0.10717	-0.4662	84.4	0.07528
	-0.9027	31.9	0.27740	-0.5502	34.0	0.20925
	-1.4484	20.4	0.40528	-0.9817	20.3	0.31342
	-0.8129	69.6	0.15866	-0.5260	71.8	0.08695

Assuming the true treatment effect of GSK2245035 is no worse than the results from the AstraZeneca study and 20 subjects complete follow up assessments the probability of meeting the success criteria for Min LAR and WM LAR are approximately 78% and 81% respectively. This is considered sufficient justification for requiring 20 completers.

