#### **4.4. Design Justification**

- GSK2245035 is currently being developed for patients with allergic asthma. It has been studied in healthy volunteers (HVT) and subjects with allergic rhinitis with and without mild asthma.
- This study will assess the safety, target engagement, and efficacy of GSK2245035 in subjects with allergic asthma using a placebo-controlled, parallel group design and a BAC model. The BAC model is an established methodology and will be used in this study to determine whether 8 weekly doses of 20 ng i.n. GSK2245035 attenuates allergen-induced asthmatic responses compared to placebo. In addition to the assessment after BAC at the end of the 8-week treatment (1 week after the 8th dose), additional BACs will be performed at approximately 4 weeks and 12 weeks after the 8th dose to assess the durability of the effect.
- In an 8-week repeat dose safety study TL7116958 [GlaxoSmithKline Document Number [2013N174200\\_00](#)], there was a reduction of TNSS at 15 minutes post-NAC. This could indicate an effect of GSK2245035 treatment on mast cell activation and mediator release. In the current study, nasal lining fluid will be collected before and up to 5 minutes after nasal allergen challenges to evaluate the impact of GSK2245035 on mast cell mediator release. NACs will be performed approximately 24 hours after the BACs that are conducted at screening and at approximately 1 week and 4 weeks after the final dose.
- Interim analysis: Previous experience within GSK suggests some individuals (approximately 20%) fail to demonstrate a LAR response after the screening visit (i.e. they pass the screening criteria but do not demonstrate another LAR response when receiving placebo during the on-treatment phase). Those GSK studies were mainly crossover designs with a placebo in every sequence, so subjects who did not demonstrate a post screening LAR could be retrospectively identified and excluded from the statistical analyses. However this study has parallel groups and the profiles of a “perfect” drug effect and an inconsistent LAR subject are indistinguishable so retrospective exclusions cannot be made for the GSK2245035 arm. If the rate of “non-reproducible LAR” subjects is large it will reduce the probability of success.

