**Table 3**      **Lookup table for Interim Analysis Decision Pathway**

Assessing impact of non-LAR response rate: To evaluate whether recruiting additional subjects may counteract the impact of the non-LAR responder alternative version(s) of Table 3 would be constructed, but using final sample sizes that range from 20 to 30 subjects per arm. If any of the resulting estimates for probability of success are within 10% of the original operating characteristic the study may continue; but requiring additional subjects (the smallest number that satisfied the continuation criteria). In addition posterior distributions for the percentage attenuation of the primary endpoints by GSK2245035 would be constructed from the available interim data.

Amending protocol / termination of further enrolment (existing subjects would complete the study as planned): If the median (point estimate) for the observed treatment effect is dramatically different to the assumed effect from the AZ study, the study team may wish to predict the probability of success at the end of the study from the interim information (details to be provided in the RAP). If this updated probability of success is low then the study team may review any of the other available data items at the interim prior to amending the protocol / terminating further enrolment (and share these outputs with appropriate internal GSK governance boards / senior management).

To determine the probability of success in the presence of non-LAR responders (for each of the primary endpoints) simulations were performed for each possible combination of number of available placebo subjects (n) and number showing no LAR response (r) using the AZ point estimates as the true percentage attenuation:

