The rate of non-LAR response (p) was assumed to be the same for Placebo and GSK2245035 arms. A Beta(0.1, 0.1) prior distribution was assumed for the rate, which was updated using conjugate formulae as Beta( $0.1 + r$ ,  $0.1 + n - r$ ) and a value sampled from this posterior distribution. The number of future subjects on placebo with a non-LAR response was sampled from a Binomial distribution using the sampled value of p and ( $20 - n$ ) observations (the total is a mixture of observed interim data and this sampled value). Similarly the number of non-LAR responders on the GSK2245035 arm was sampled from a Binomial distribution with the same value of p and 20 observations. Each non-responding individual was assigned a constant value for the response, and the collection of non-responders were combined with the collection of LAR responders (generated in a similar way using the random effects meta-analysis to obtain the expected responses). The probability of success was determined for each of the combined datasets and the median was derived. If this median was more than 10% smaller than the original operating characteristic the recommendation is to further review the data. The recommendations from the two endpoints were combined into a single table. Wherever there was disagreement between cells the review data decision was chosen.

Sensitivity analyses showed the outcome of this approach is highly dependent on the value of the constant used for the non-LAR responses (the further the choice from the range of plausible values for LAR responders the more likely the recommendation was to review data). The choice of value is arbitrary in nature, but was selected as -0.45 for Minimum Change From Saline and -0.2 for Weighted Mean Minimum Change From Saline, based upon applying the LAR criteria to seven historical studies and deriving the mean responses of all non-LAR responding subjects. Since the decision tables cover all interim study possibilities and is pre-specified the consequences of this arbitrary choice can be articulated.

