To evaluate whether recruiting additional subjects may counteract the impact of the non-LAR responders alternative version(s) of [Table 1](#) were constructed using the same methodology, but using final sample sizes that range from 20 to 30 subjects per arm. At each cell, if the probability of success was within 10% of the original operating characteristic for that endpoint (i.e. the characteristics derived under the assumption of zero non-LAR responders) the study would continue; but requiring additional subjects (the smallest number that satisfied the continuation criteria). These additional tables have been compressed into [Table 2](#), which shows the smallest number of subjects (per arm) required to continue the study (if the continuation criteria were still not met with 30 subjects per arm the cell is flagged as recommending further data review).

Table 2 Lookup Table for Interim decision and revised sample sizes (per arm)

Additional analyses / outputs to support the interim analysis decision making

Equivalent versions of the planned summary statistics and figures supporting the primary endpoint/analyses.

Posterior distributions for the percentage attenuation of the primary endpoints (WM and Minimum LAR at FUV1) by GSK2245035 would be constructed from the available interim data using the same methodology as for the planned final analysis; except that a simplifying assumption will be used and terms relating to allergen exposure in the model will be excluded; since there may not be enough information in each strata at the time of the interim to facilitate their estimation (see Section 7 for details of the planned Primary analysis).

Non-binding “Rule of thumb” for amending protocol/termination of further enrolment (existing subjects would complete the study as planned)

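### The 78%/81% probabilities of success behind 20 completers per arm hold only with zero non-LAR responders, a condition Protocol 9.2.1 does not state; at the roughly 20% rate in Protocol 4.4 they are about 70%/74% or 73%/76%

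*Protocol*

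**What the plan says.** Protocol 9.2.1 takes a true effect no worse than that of the cited AstraZeneca (AZ) study and 20 completers per arm, and concludes that "the probability of meeting the success criteria for Min LAR and WM LAR are approximately 78% and 81% respectively". It treats this as adequate grounds for 20 completers. Its other stated condition is that "the behaviour of the placebo response and the variability of the endpoints in this study are similar to the eight historical GSK studies". Subjects who lose their LAR after screening are not mentioned in 9.2.1. The sensitivity grid in 9.2.2 varies only the success threshold, the sample size and the attenuation.

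Protocol 4.4 reports that "some individuals (approximately 20%) fail to demonstrate a LAR response after the screening visit". In the earlier, mainly crossover, studies "subjects who did not demonstrate a post screening LAR could be retrospectively identified and excluded from the statistical analyses". In this parallel-group trial they cannot be removed from the active arm, and 4.4 acknowledges that a large rate lowers the chance of success.

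The interim analysis (Protocol 9.3.2, SAP 3.1) compares the projected probability of success with the original operating characteristic, which SAP 3.1 describes as "the characteristics derived under the assumption of zero non-LAR responders". The interim simulation runs "using the AZ point estimates as the true percentage attenuation", gives non-LAR subjects a constant response (-0.45 for Min, -0.20 for WM) at the same rate in both arms, and in it "the collection of non-responders were combined with the collection of LAR responders". The responders are generated from the same meta-analysis that underlies Table 2. The plan can extend to at most 30 per arm.

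**The concern.** The planning figure in 9.2.1 sets to zero a rate that the same protocol puts at about 20%. Only the SAP says so explicitly. Non-LAR subjects in both arms shrink the mean difference and leave less to attenuate.

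A governance or ethics reader of 9.2.1 would take about 80% as the chance of success per endpoint with 20 per arm. Whether 20 per arm gives that at the expected rate depends on two things 9.2.1 leaves open: whether Table 2 includes non-LAR subjects, and whether the AZ attenuations of 18% (Min) and 27% (WM) describe LAR responders or whole arms.

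**Working it through.** **Inputs.** Success means a posterior probability of any attenuation above 0.7, equivalent to a one-sided test at 0.30 (Protocol 9.2). True attenuations are 18%/27%. The simple means of the eight Table 2 placebo responses are -1.0504 (Min) and -0.6558 (WM). Residual variability is read as a variance; read as an SD it would give 98%/99.8%.

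**Formula.** With n per arm, mean difference D and variance V, the probability of success is P(T > t) for a noncentral t with 2n-2 df, noncentrality D/√(2V/n) and t the 0.70 quantile.

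**Step 1: reproduce the plan's figures (zero non-LAR, n=20).**
- D = 0.18 × 1.0504 = 0.1891 (Min) and 0.27 × 0.6558 = 0.1771 (WM).
- Between the simple-mean and df-weighted variances (Min 0.233 and 0.188; WM 0.164 and 0.130), the result is 76.2–80.3% for Min and 80.4–84.8% for WM. The stated 78%/81% lie inside these ranges.
- Variances that give exactly 78%/81% are 0.2119 and 0.1588. They are used below.

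**Step 2: the sponsor's interim model at a 20% rate in both arms, attenuation applied to responders.** D is multiplied by 0.8. V = 0.8·s² + 0.16 × the average over arms of (responder mean − constant)².
- Min: D = 0.8 × 0.1891 = 0.1513. V = 0.8 × 0.2119 + 0.16 × (0.3605 + 0.1692)/2 = 0.2119. Noncentrality 1.039, giving 69.6%.
- WM: D = 0.8 × 0.1771 = 0.1416. V = 0.8 × 0.1588 + 0.16 × (0.2077 + 0.0777)/2 = 0.1499. Noncentrality 1.157, giving 73.6%.
- The placebo arm means become -0.930/-0.565, so the whole-arm attenuation falls to 0.1513/0.930 = 16.3% and 0.1416/0.565 = 25.1%.
- A 40,000-trial simulation gives 69.8%/74.0%.

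**Step 3: 18%/27% as whole-arm averages.** D = 0.18 × 0.930 = 0.1675 and 0.27 × 0.565 = 0.1524. The result is 73.5%/76.5% (simulation 73.2%/76.2%).

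SAP 7.1.2 bears on this for WM. Its AZ-based prior has an active mean of -0.7081 (variance 0.4472²/26). The placebo mean is -0.7081 − 0.2619 = -0.9700 (total variance 0.4472²/25). The attenuation is 0.2619/0.9700 = 27.0%, the planning value, built from two arm means.

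**Step 4: Table 2 already contains 20% non-LAR subjects.** Responder means are then (-1.0504 + 0.2 × 0.45)/0.8 = -1.200 and (-0.6558 + 0.2 × 0.20)/0.8 = -0.770, with variances 0.152/0.134.

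| Case at a 20% rate (Min/WM) | 20 per arm | 30 per arm |
|---|---|---|
| Interim model, attenuation on responders | 70%/74% | 77%/81% |
| Attenuation a whole-arm average | 73%/76% | 81%/84% |
| Table 2 already includes non-LAR subjects | 77%/81% | not computed |
| Both of the last two | 80%/83% | not computed |

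**Sensitivity of the first row at 20 per arm.**
- Varying the constants over an assumed range (-0.25 to -0.65 for Min, 0 to -0.40 for WM) gives 67–72%/70–76%.
- Varying the constants and the variance choice together gives 65–74%/70–80%.
- Simulating interim counts near 20% (2/10, 3/14, 3/15, 4/20) gives 66–71%/72–76%.
- A 10% rate gives 74%/77%; a 30% rate gives 66%/70%.

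**The case against.** **The figures are not wrong, and the condition is disclosed.** This stands. A reader might infer a calculation error in 9.2.1, but the stated values reproduce from Table 2. The condition is in the SAP, however, not beside the figure it qualifies.

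**70%/74% is the worst of four cases.** This stands in part. Protocol 9.2.1 conditions on the AZ result, which reads most naturally as a trial-level effect. The two-arm prior in SAP 7.1.2 points the same way for WM, although it does not say whether non-LAR subjects were excluded. That supports 73%/76%, a loss of 4.5 points on each endpoint. A reader might therefore infer that the true chance is 70%/74%; the documents do not settle that.

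The two cases with little or no loss need Table 2 to include non-LAR subjects. Protocol 4.4 says only that exclusion was possible. Inclusion would conflict with the zero-rate statement in SAP 3.1, and the interim model would then add non-responders to a population that already contained them.

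**The interim analysis manages the risk.** It does, with an extension to at most 30 per arm, and 9.2.3 points to it. Sites are also encouraged to screen subjects with a known LAR (Protocol 5.3), which may lower the rate. A reader might infer that the trial is undersized or the risk ignored; neither follows. But the loss on the interim model is 8.4/7.4 points (0.084/0.780 = 10.8% and 0.074/0.810 = 9.1% relative), close to the sponsor's 10% review trigger. The expected rate may therefore not lead to more subjects.

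**Success on either endpoint is likelier.** SAP 3.1 uses that rule for its end-of-study prediction. At an assumed correlation of 0.7–0.9, 69.6%/73.6% becomes 78–82%. Protocol 9.2.1 quotes per-endpoint values, so the comparison here is per endpoint.

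**The lookup tables may show more.** Figures 1–4 and the bodies of Protocol Table 3 and SAP Tables 1–2 were not legible in the text examined. Nothing here relies on their contents.

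**Conclusion.** The point holds as an unstated condition on a planning figure, not as an arithmetic error. The 78%/81% are correct for zero non-LAR responders. At the rate reported in Protocol 4.4, with 20 per arm and no extension, the per-endpoint values are about 70%/74% on the interim model, or about 73%/76% if the AZ attenuations are whole-arm averages. Extending to 30 per arm brings them to about 77%/81% and 81%/84%.

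These values assume equal rates in both arms, variances calibrated to 78%/81%, and the sponsor's constants. Protocol 9.3.2 calls the choice of constants arbitrary and the interim outcome "highly dependent on the value of the constant used for the non-LAR responses". If Table 2 already includes about 20% non-LAR subjects there is almost no loss; only the sponsor can confirm this. Confidence in the size of the loss is medium. The documents do not support concluding that the sample size must change.

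**What to change.** In Protocol 9.2.1:

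1. State that 78%/81% assume zero non-LAR responders.
2. Report the per-endpoint probability of success at a 20% rate for 20 and 30 per arm, as a range over the non-LAR constant and over responder-level versus whole-arm attenuation.
3. State whether the Table 2 inputs and the AZ attenuations include non-LAR subjects. If Table 2 does, reconcile this with SAP 3.1 and the interim model.
4. Cross-refer to 9.3.2 for the interim extension.

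Sample size, lookup tables and decision rules do not change. The cost is a run of the existing simulation at these settings and a few sentences. The quoted figure may become less favourable, and it has to carry a range because it depends on the constant.
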